## 5. Number of Subjects

5.1. This is a single-center study at the University of New Mexico, therefore the total number of subjects at the University of New Mexico is the total number of subjects for the study.

5.2. The total number of subjects to be recruited at this site is up to 130 patients.

5.3. *Sample size calculation:* The primary outcome for this study is the change in the OAB-q total score from baseline to 3 months. We used the means and standard deviation for this questionnaire from an unpublished pilot RCT study from Walter Reed that compares PTNS and TENS for the treatment of OAB (unpublished work). We have powered the study based on a 10-point difference as significant between groups. This 10-point difference used for the power calculation is based on the previously established minimum important difference. To achieve power for this non-inferiority RCT study showing that the difference between groups is less than 10 points, we need 40 patients per group (80 total) to detect no difference with  $\alpha = 0.05$  and 80% power. Allowing for dropout of up to 30%, we will aim to randomize 114 patients, and will plan to recruit up to 130 to allow for potentially higher drop-out, as the study primary outcome is at the 12 weeks' time point. As we plan to perform both per-protocol and intention-to-treat analysis, the sample size must be met for both per-protocol and intention-to-treat analysis, with the per-protocol patients (those in the PTNS group completing at 12 treatments in a total of 13 weeks) being expected to be a lower sample size.

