PROTOCOL TITLE: INTENSE: INvestigation of TENS Efficacy versus Posterior Tibial Nerve Stimulation for overactive bladder

given a 3-day voiding diary to complete prior to starting their intervention. Urinalysis and urine culture will be obtained to rule out urinary tract infection. This is routinely done on all new patients in our clinic and would be performed on patients not participating in the study as well. Data collected in addition to the above outcome measures includes patient demographics, medical/surgical history, and contact information, which are attached as supporting documents. This information will be collected from the patient on the day of enrollment and we will review the patient's medical record if information is missing or unclear.

The randomization sequence will be generated by computer-based randomization in a sequence that preserves 1:1 randomization and also preserves allocation concealment (likely with randomly alternating block sizes of 6-10 in blocked randomization). Randomization assignments will be completed via REDCAP by a research coordinator. Randomization will only occur after consent has been signed and all baseline data has been obtained.

*12.1. Interventions:*

*12.1.1. PTNS:* Women randomized to the PTNS group will begin therapy after their baseline evaluation is complete. They will be scheduled for PTNS treatment sessions once weekly for 30 minutes, for 12 weeks total. PTNS treatment will be performed as follows:

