- The patient sits in a reclining chair, with their legs elevated on a foot rest. The area for needle placement is cleaned with an alcohol swab. A 34 gauge needle is inserted percutaneously approximately 5 cm cephalad to the medial malleolus of the right or left ankle (patient's choice) at a 60 degree angle. A surface electrode is placed on the medial aspect of the ipsilateral calcaneus. The needle and electrode are connected to a low voltage (9V) electrical stimulator (brand name). Stimulation current with a fixed frequency of 20 Hz and a pulse width of 200  $\mu$ sec is increased until flexion of the big toe or fanning of all toes visualized, or until the woman reports a tingling sensation across the heel or sole of the foot. The current is then set to the highest level of tolerable to the patient (0-10 mA) and then she undergoes therapy for 30 minutes. If no response is seen (no fanning of toes or flexion of big toe or no report of a tingling sensation across the heel or bottom of the foot), the needle is replaced on the same or opposite side until the appropriate response is seen. The needle placement sites will be monitored for bleeding, bruising, irritation or a hematoma. This will be repeated each week, until the completion of 12 weeks of treatment.
- If women assigned to the PTNS arm miss one of their weekly office PTNS sessions, they will be permitted to "make up" the missed session at the end of the 12 weeks, and their "12 week" outcome measures will be performed following that last session (13 weeks following randomization). Women that have missed this one session and made up the session at the end of the treatment course will be considered "fully compliant" with treatment and analyzed in the "per protocol" analysis as having completed the PTNS treatment course per protocol.
- If women assigned to the PTNS arm miss more than one of their weekly office PTNS sessions, they will not be allowed to make up the extra sessions and their

PROTOCOL TITLE: INTENSE: INvestigation of TENS Efficacy versus Posterior Tibial Nerve Stimulation for overactive bladder

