participation in the study or outcome measurement will not be extended further than 13 weeks after randomization. However, they will not be withdrawn from the study for missing sessions, and will be followed for outcomes and adverse events despite missing sessions of PTNS. Women that miss more than one session of PTNS or miss one session and do not make it up at the end will be considered “not fully compliant” with PTNS treatment, and will be analyzed in the “intention-to-treat” analysis in the PTNS arm but not in the “per protocol” analysis in the PTNS arm.

Prior to their week 6 session, women will be asked to complete a 3-day voiding diary in the three days before their scheduled PTNS treatment and bring it to clinic. At their week 6 session, women will complete the UDI and PSQ questionnaires via REDCAP on an iPad in clinic. The same will be conducted for their week 12 session. Patient compliance of attending PTNS sessions will be recorded.

**12.1.2. TENS:** Women randomized to the TENS groups will begin therapy after their baseline evaluation is complete. They will be asked to purchase a TENS 7000 device (estimated cost \$30) and will administer self-treatment at home, daily for 20 minutes, for 12 weeks total. Current practice in the Urogynecology clinic is to offer TENS therapy to women as an alternative to in-person maintenance therapy for after completing PTNS 12 sessions. TENS 7000 device is off label for its use in the treatment of OAB. If funding is secured, women in both PTNS and TENS group will be reimbursed with a merchandise card. Participants will be asked to bring their device to clinic to ensure the correct device is used, standardize settings and provide the following patient education:

- Proper TENS device set up and pre-set standardized settings, detailed below
- Proper electrode pad placement that will be demonstrated. Electrodes will be traced with a skin marker during this clinic visit and pictures will be provided to ensure correct placement at home. If the patient has a camera, they can photograph electrode placement while in clinic.
- Determine intensity level
- Patients will be notified that they can go about their regular daily activities with the TENS device in place, so that treatment does not interfere with normal work or household duties. However, they will be instructed to not use the device while exercising due to sweat causing reduced adhesive function of electrodes and possible displacement.

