- If a caretaker will be assisting the participant in use of the TENS unit due to physical limitations, they too will be instructed in set-up and use.
- An information handout with device settings, surface electrode placement, and treatment schedule will be provided at this initial clinic visit.

TENS treatment will be performed as follows (adapted from the most common setting from a systematic review of TENS for OAB):

- Surface electrodes, 2 x 2 in diameter, will be placed 5 cm cephalad to the medial malleolus of the right or left ankle (patient’s choice). The second surface electrode is placed on the medial aspect of the ipsilateral calcaneus. The electrodes are connected to the TENS device with the following pre-set settings:
- Mode: “M” or modulation

PROTOCOL TITLE: INTENSE: INvestigation of TENS Efficacy versus Posterior Tibial Nerve Stimulation for overactive bladder

- Frequency: 10 Hz
- Pulse width: 200  $\mu$ sec
- Intensity: to patient comfort level, as determined at clinic visit when device is verified. This is variable and participants will be told that as they use the device regularly, it is anticipated that they will become accustomed to stimulation and may need to change this setting.
- Women will then complete 20-minute daily TENS treatment using the settings above, for 12 weeks total.
- If women assigned to the TENS arm miss more than 2 daily sessions in a week on one of their weeks of treatment, they will be permitted to “make up” the missed sessions with an extra week of treatment at the end of the 12 weeks, and their “12 week” outcome measures will be performed following that week of make-up (13 weeks following randomization). Women that had this one “deficient week” with less than 5 treatments in a week and made up a week (with 5 or more daily treatments in the last week), their treatment course will be considered “fully compliant” with treatment and analyzed in the “per protocol” analysis as having completed the TENS treatment course per protocol.

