### 13.Data Analysis

- 13.1. *Data Analysis:* Between and within group differences will be evaluated using Fisher's exact test for categorical variables and t-tests for continuous variables, as we expect the data will be normally distributed. Wilcoxon rank-sum test will be used for continuous variables that are not normally distributed. If there are any baseline differences between groups, a multivariate analysis will determine the contribution of these differences to observed differences (if any) between groups.
- 13.2. *Intention-to-treat analysis:* We plan to perform the primary analysis as "intention-to-treat" indicating that patients will be analyzed in the group to which they were randomized, regardless of compliance with study procedures, unless they asked to be withdrawn or were withdrawn by investigators due to safety or validity concerns. For example, PTNS patients that miss more than one session or do not make up a missed session of their office PTNS would still be analyzed in the "intention-to-treat" analysis as being in the PTNS group.
- 13.3. *Per protocol analysis:* We plan to perform a secondary analysis as "per protocol" indicating that patients will be analyzed in the group to which they were randomized only if they complete a full 12 weeks of treatment in compliance with study procedures, meaning that women assigned to the PTNS arm completed 12 weekly PTNS sessions in the office in 13 weeks or less, and women in the at-home TENS arm performed TENS stimulation at least 5 days per week for 12 weeks, as averaged over 12 weeks. For example, PTNS patients that miss more than one session or do not make up a missed session of their office PTNS will not be analyzed in the "per protocol" analysis as being in the PTNS group.
- 13.4. *Power Analysis:* Power analysis was performed based on previously reported means and standard deviation for the OAB-q. The primary outcome of this study is improvement in HRQL and symptom bother of OAB/UUI as measured by the OAB-q. We used the means and standard deviation for this questionnaire from a prior unpublished pilot RCT from Walter Reed comparing PTNS and TENS for the treatment of OAB. We have assumed a change score of greater than 10 points to be significant between groups based on the minimally important difference that has been previously established. To achieve significance for a non-inferiority study using these assumptions we would need 80 patients,

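### The per-protocol set requires 12 of 12 sessions from PTNS women but about 71% of sessions from TENS women, with no rationale; a supportive set with similar fractions is needed

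*Combined protocol and SAP*

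**What the plan says.** PTNS is given "once weekly for 30 minutes, for 12 weeks total" (Section 12.1.1), so 12 sessions are scheduled. Section 13.3 admits a PTNS woman to the per-protocol set if she "women assigned to the PTNS arm completed 12 weekly PTNS sessions in the office in 13 weeks or less". Section 12.1.1 explains the thirteenth week: one missed session may be made up, and such a woman counts as fully compliant. The group described as "Women that miss more than one session of PTNS or miss one session and do not make it up at the end" is left out of the per-protocol set but kept in the intention-to-treat analysis.

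TENS is daily for 12 weeks (Section 12.1.2), so 84 sessions are scheduled. Section 13.3 admits a TENS woman if she "performed TENS stimulation at least 5 days per week for 12 weeks, as averaged over 12 weeks". Section 12.1.2 also has a make-up week for one deficient week.

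Intention-to-treat is primary (13.2) and per-protocol is secondary (13.3). Section 5.3 nevertheless states that "the sample size must be met for both per-protocol and intention-to-treat analysis". Section 13.4 repeats this for power and expects a smaller per-protocol set that will need more recruitment and follow-up.

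**The concern.** The two arms of one comparison are filtered to different standards. A PTNS woman at 11 of 12 (92%) with no make-up is removed, while a TENS woman at 60 of 84 (71%) is kept. The retained PTNS women are therefore the more selected group. If adherence is related to outcome, that selection produces a difference even when the treatments work equally well.

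In a non-inferiority trial the per-protocol result is the usual check on intention-to-treat, and this plan asks for full sample size in both. A check that carries its own selection difference is hard to read when it disagrees with the primary result, and gives less reassurance than it seems to when it agrees.

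**Working it through.** **1. The plan's own figures.** 80 / (1 − 0.30) = 114.3, which matches the stated 114. The 40 per group cannot be reproduced because no SD is given. Back-solving with margin 10, true difference 0 and 80% power: SD = 10 × √20 / (z₁₋α + 0.842). This is 18.0 at one-sided 0.05 and 16.0 at one-sided 0.025; the plan does not state sidedness. SD 18 and one-sided 0.05 are used below.

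**2. The thresholds.** PTNS: 12/12 = 100%, with or without the make-up. TENS: (5 × 12)/(7 × 12) = 60/84 = 71.4%, so 24 sessions may be missed. Under the make-up-week rule in 12.1.2 the TENS floor is 60 of 91 days (66%). The asymmetry stands on either reading.

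**3. Who qualifies at equal adherence.** Assume each session is attended independently with probability p. PTNS: p¹² + 12(1 − p)p¹², where the second term is one session missed and made up. TENS: P(Binomial(84, p) ≥ 60).

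| p | PTNS, present rule | TENS, present rule | PTNS if 9 of 12 |
|---|---|---|---|
| 0.85 | 40% | about 100% | 91% |
| 0.90 | 62% | about 100% | 97% |
| 0.95 | 86% | about 100% | 99.8% |

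**4. Size of the shift.** Now let p vary between women as a beta distribution, mean 0.90, concentration 20 (SD of p = √(0.9 × 0.1/21) = 0.0655), the same in both arms, with no true difference. Averaging the step 3 formulas over this distribution, 64% of PTNS and 98% of TENS women qualify, with mean p among them of 0.9253 and 0.9038.

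Shift = correlation × SD × (difference in mean p) / (SD of p). At correlation 0.3: 0.3 × 18 × 0.0215 / 0.0655 = 1.77 points. At 0.2 and 0.4 it is 1.2 and 2.4. With 9 of 12 for PTNS, 94% and 98% qualify and the shift at 0.3 is 0.2. At correlation 0.3, with mean adherence from 0.85 to 0.95 and concentration from 10 to 100, the present rule gives 0.6 to 2.1 points and the common-fraction rule at most about 0.3.

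**5. Power at correlation 0.3.** Power = Φ((10 − shift)/SE − 1.645).
- 40 per arm in the per-protocol set, as 5.3 requires: SE = 18√(2/40) = 4.02; Φ(8.23/4.02 − 1.645) = about 65%.
- 40 per arm before per-protocol exclusions (40 × 0.644 = 26 PTNS, 40 × 0.981 = 39 TENS): SE = 4.57; about 56%. Lost numbers alone, with no shift, give about 71%.
- 40 per arm before exclusions, with 9 of 12 for PTNS: SE = 4.11; about 77%.

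**6. The other sign.** If less adherent women do better, for instance because they stop coming once improved, the shift favours TENS by the same amount. With a true deficit at the margin and 40 per arm, the chance of a false per-protocol non-inferiority result becomes Φ(1.77/4.02 − 1.645) = about 11% instead of 5%.

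**7. Room for exclusions.** 57 per arm less 30% is 39.9, so almost any non-compliance among PTNS completers takes that arm below 40. At 65 per arm, 45.5 complete and 40/45.5 = 88% must be fully compliant. The 30% is described as dropout; no compliance rate is given.

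**The case against.** Per-protocol is expressly secondary, and every excluded PTNS woman stays in the primary analysis. The plan foresees the smaller set and allows for more recruitment. A shift of about 2 points is small beside a 10-point margin, and if adherent women do better it works against TENS and so cannot help a false claim. Adherence, correlation and SD are all assumed, and equal adherence in both arms sits awkwardly with the plan's own hypothesis of better compliance with TENS. Twelve clinic sessions of 30 minutes and 84 home sessions of 20 minutes differ in kind, so an equal fraction is not shown to be an equal standard. Loosening the rule for the reference arm could dilute the comparator and favour non-inferiority. Section 13.1 already plans a multivariate analysis if baseline differences appear.

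Much of this stands. It limits the point to the per-protocol set, makes the sizes illustrative, and argues against replacing the strict rule. It does not supply a rationale for the different thresholds. Extra recruitment restores numbers but not comparability, and the conservative direction is only one of two possibilities. The adjustment in 13.1 is conditional and names no covariate.

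**Conclusion.** The point holds as an asymmetry of selection in the secondary analysis: 100% against 71% of scheduled sessions, unexplained, in a set that the plan says must reach full sample size and power. That part is read directly from the text. The illustrative size is a spurious difference of about 1.2 to 2.4 points. At correlation 0.3, per-protocol power is about 65% if 40 per arm are reached in that set, or about 56% if 40 per arm is the count before exclusions. These figures rest on equal mean adherence of 90% with the spread given above, correlations of 0.2 to 0.4 and SD 18, none of which the documents state.

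A reader might infer more, and the documents do not support it. The PTNS data are not thrown away: 12.1.1 and 13.2 keep these women in the primary analysis. The per-protocol result is not shown to be biased against TENS, since the sign cannot be fixed. Nor is 56% the power of the plan as written, because 5.3 requires the numbers to be met in the per-protocol set and 13.4 expects further recruitment to get there. The strict PTNS rule is not shown to be wrong; what is missing is a comparison that applies similar standards to both arms.

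**What to change.** In Section 13.3:
- Keep the present definition as the main per-protocol set and give the reason for its thresholds.
- Pre-specify a supportive per-protocol set with a similar minimum fraction of scheduled sessions in both arms, for example at least 60 of 84 and at least 9 of 12 (12 × 5/7 = 8.57, rounded up; 75% against 71%).
- Adjust the per-protocol comparisons for baseline OAB-q, which is already collected. This removes only the part of the selection that the baseline score explains.
- State that the per-protocol result is read as robust only if both sets agree with the intention-to-treat result.

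Make the definitions in 5.3, 12.1.1, 12.1.2 and 13.4 consistent with 13.3. Two passages in 12.1.2 need reconciling: the TENS rule is given both week by week with a make-up week and as a 12-week average, and non-compliant TENS women are said to be left out of the per-protocol analysis of the PTNS arm.

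The cost is some wording and one extra analysis. The looser set admits PTNS women with fewer sessions, which could dilute the comparator and favour non-inferiority, so it should be supportive only. This changes analysis sets, not treatment schedules.

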#### **14. Provisions to Monitor the Data to Ensure the Safety of Subjects**

There is no DSMB that will be monitoring safety of these procedures as the study risks are low. PTNS is a common treatment modality for OAB and UUI and standard of care with minimal adverse effects. TENS for OAB and UUI has been shown to be a low-risk intervention with minimal adverse effects. Skin irritation, a “shocking” sensation, or temporary pain with stimulation could be experienced. Additionally, we will keep track of adverse events by asking patients about adverse effects at each weekly treatment session for the PTNS group and in weekly phone or email reminders for the TENS group during the course of the study. Because neither of the studied treatments are experimental or associated with above average risk we do not anticipate any significant adverse events. Participants will have access to a 24/7 phone number to reach research or clinical staff with concerns. All adverse events will be recorded in REDCap and reported to the study PI.

We do not anticipate any conditions that would trigger a suspension or termination of the research.

#### **15. Withdrawal of Subjects**

Participants may withdraw from the study at any time without penalty and will continue to receive the clinical standard of care. A subject may be withdrawn from the study without her consent at the discretion of the physician and study staff if they believe she no longer meets study inclusion criteria or if she meets exclusion criteria, if they believe that it is not in her best interest to continue study participation i.e., desire to undergo alternative treatment, or if they stop the study early due to scientific reasons. Investigators may withdraw a subject if the subject is not following the study protocol. If a woman is withdrawn from the study either at her own discretion or that of the research staff, she may continue with conservative or surgical management of her OAB/UUI in the usual fashion. If a participant chooses to withdraw from the study, the study intervention and PTNS device will no longer be provided to the participant and may not be available for purchase. If a participant withdraws from the TENS group, the TENS device they purchased will be kept by the participant.

To minimize withdrawal from the study, patients will be randomized after they have had what they feel to have been adequate time to consider whether or not they would like to participate in the study and they provide consent. According to the 2010 CONSORT guidelines, we will analyze all participants assessed for eligibility within the study. We will document reasons for withdrawal from the study if the participant willingly provides this

PROTOCOL TITLE: INTENSE: INvestigation of TENS Efficacy versus Posterior Tibial Nerve Stimulation for overactive bladder

information. We will report eligibility criteria not met or reasons for declining participation in the study if the participant willingly provides this information. The withdrawal procedure is clearly documented in the study consent.

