### **3. Study Design**

We plan to perform an unmasked, non-inferiority randomized controlled trial to determine if the quality of life is improved with the use of TENS compared to PTNS for urgency urinary incontinence and overactive bladder. The target population is patients with OAB and/or urgency urinary incontinence (UUI) who present to the urogynecology clinic either at the University of New Mexico Hospital (UNMH) or Sandoval Regional Medical Center (SRMC). Women will be informed of the arm of the study to which they are randomized, as the intervention is unable to be masked. Masking is not possible with this study design due to the nature of the interventions. All women will give written consent prior to enrollment.

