4.2.1. Inclusion Criteria

- Female Subjects  $\geq 18$  years of age
- OAB, UUI or Mixed Urinary Incontinence with urgency predominant symptoms and more bother from UUI than stress urinary incontinence
- Failed trial of conservative therapy (including bladder training, fluid modification, diet modification, caffeine restriction, or pelvic floor training)
- Failed trial of at least one pharmacologic treatment (anticholinergics,  $\beta 3$ -adrenoceptor agonist) either due to inability to take the medication, adverse reaction to medication, or no improvement on medication
- Willing to complete study questionnaires
- Willing to adhere to 12 office visits for PTNS over 3 months if randomized to that arm
- No contraindication to undergoing PTNS or TENS therapy

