4.2.2. Exclusion Criteria

- Age  $< 18$  years
- Presence of urinary fistula
- Male genital anatomy
- Undergoing evaluation or treatment of recurrent (2 or more infections in the last 6 months or 3 or more infections in the last 12 months) or current urinary tract infection
- Current Bladder stones
- Bladder cancer or suspected bladder cancer
- Gross Hematuria
- Pregnancy or planning to become pregnant during the study
- Cognitive impairment
- Central or peripheral neurologic disorders such as multiple sclerosis, Parkinson's disease, spina bifida, spinal cord lesions, etc.
- Metal implants such as pacemaker, implantable defibrillator, or metal implants where PTNS or TENS device needs to be placed (ankle/leg)
- Uncontrolled diabetes
- Diabetes with peripheral nerve involvement

PROTOCOL TITLE: INTENSE: INvestigation of TENS Efficacy versus Posterior Tibial Nerve Stimulation for overactive bladder

- Current use of anticoagulants (excluding aspirin)
- Current use of anticholinergics or use within the last 4 weeks
- Current use of botox bladder injections or bladder botox injection within the last year (12 months)
- Current use of sacral neuromodulation therapy or currently implanted sacral neuromodulation device or leads
- Bladder outlet obstruction
- Urinary retention or gastric retention
- Painful Bladder Syndrome/Interstitial Cystitis
- Unable to be contacted for follow up by telephone
- Inability to speak/read/understand English or Spanish

4.3. We have decided to only include adults (age  $\geq 18$  years) who are capable of giving informed consent. Children, pregnant women and prisoners will be excluded.

4.4. We will include English and Spanish speaking populations only, as our primary outcome measures have not been validated in other languages. We are excluding men as we are a Urogynecology practice and therefore do not treat that population.

4.4.1. Because we are excluding pregnant women, during participant recruitment women will be asked if they are pregnant or have plans to become pregnant in the next 3 months. Their sexual activity, menopause status and surgical history (specifically hysterectomy or tubal ligation) will also be determined, which are standard questions asked in our practice for new patients. If there is concern for pregnancy, we will perform a urine pregnancy test of the participant on the day of enrollment.

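### Section 15 lets unmasked staff withdraw a woman for an entry criterion she fails only after randomisation, and the plan provides no week-12 outcome for her

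*Combined protocol and SAP*

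**What the plan says.** Section 15 (Withdrawal of Subjects) gives staff a discretionary power: "A subject may be withdrawn from the study without her consent at the discretion of the physician and study staff". One ground is "if they believe she no longer meets study inclusion criteria or if she meets exclusion criteria". The same sentence adds the woman's best interest as a ground and gives a wish for other treatment as its example. A later sentence adds not following the protocol.

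The criteria this refers to are in section 4.2. One exclusion is "Current use of anticholinergics or use within the last 4 weeks", a state that can begin after randomisation. Section 3 says of blinding: "Masking is not possible with this study design due to the nature of the interventions".

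On follow-up, sections 12.1.1 and 12.1.2 say that women who miss PTNS or TENS sessions stay in the study and are followed for outcomes. No comparable sentence covers a woman whom staff withdraw.

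On analysis, section 13.2 analyses women as randomised regardless of compliance, "unless they asked to be withdrawn or were withdrawn by investigators due to safety or validity concerns". The protocol does not define a validity concern and specifies no method for missing data.

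**The concern.** Eligibility is a property fixed at baseline. The reference to a woman who no longer qualifies reaches past errors discovered late: it covers women who were correctly enrolled and then changed. The anticholinergic criterion is the case that matters. Starting the drug after randomisation is plausibly a response to poor benefit, so the trigger is related to the primary outcome. The decision rests on what staff believe, and they know the arm.

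If such women leave the study before week 12, the women who remain are a selected group, and the selection can differ by arm. Losing failing women from TENS flatters TENS and makes a false non-inferiority claim more likely. Losing them from PTNS raises the bar for TENS and makes a true claim harder to establish. Nothing in the plan fixes which of these would dominate. The dropout allowance protects the number of women analysed; it gives no protection against selective loss.

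**Working it through.** **1. Reading the passages together.**
- Section 15: the ground is not tied to status at randomisation.
- Section 4.2.2: current anticholinergic use is an exclusion and can arise later.
- Sections 12.1.1 and 12.1.2: retention and outcome follow-up are promised for missed sessions.
- Section 13.2: some investigator withdrawals leave the intention-to-treat set. Eligibility withdrawals are not named, so whether they count as a validity concern is open.

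Together, a woman withdrawn on this ground has no stated route to a week-12 OAB-q and no defined place in the primary analysis.

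**2. The plan's own figure.** Sections 5.3 and 13.4 give a 10-point margin, 40 per group, α = 0.05 (sidedness not stated) and 80% power. Section 5.3 gives 30% dropout and 114 to be randomised. 80 / (1 − 0.30) = 114.3, so 114 reproduces.

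**3. Implied SD.** The SD comes from an unpublished pilot and is not given. Taking a true difference of zero and solving for it: SD = 10 × √(40/2) / (z₁₋α + 0.842).
- One-sided 5%: 44.72 / (1.645 + 0.842) = 17.99; SE = 17.99 × √(2/40) = 4.02.
- One-sided 2.5%: 44.72 / (1.960 + 0.842) = 15.96; SE = 15.96 × √(2/40) = 3.57.

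**4. Shift from selective removal.** Let q be the extra share of TENS women removed, and g the points by which their mean change falls short of that of the women kept. The full-arm mean equals the kept mean minus q × g, so the kept mean is too favourable by q × g. Neither q nor g is in the documents. With g = 20 assumed:
- q = 5% (about 3 of 57 randomised per arm): shift = 0.05 × 20 = 1 point.
- q = 10% (about 6 of 57): shift = 0.10 × 20 = 2 points.

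**5. False non-inferiority at a true 10-point TENS deficit**, with 40 analysed per arm: 1 − Φ(z₁₋α − shift/SE).

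| Shift | One-sided 5% | One-sided 2.5% |
|---|---|---|
| 0 | 5.0% | 2.5% |
| 1 point | 1 − Φ(1.645 − 0.249) = 8.1% | 1 − Φ(1.960 − 0.280) = 4.65% |
| 2 points | 1 − Φ(1.645 − 0.497) = 12.6% | 1 − Φ(1.960 − 0.560) = 8.1% |

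Over q = 5–15% and g = 10–30 the shift runs from 0.5 to 4.5 points, and the rates from 6.4% to 30.0% (one-sided 5%) or 3.4% to 24.2% (one-sided 2.5%).

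**6. The opposite direction.** If the removals are in PTNS only and the arms are truly equal, power is Φ((10 − shift)/SE − z₁₋α). It falls from 80% to 72% (1 point) or 63% (2 points) at one-sided 5%, and to 71% or 61% at one-sided 2.5%.

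**7. Balanced removal.** With the same q and g in both arms, the shifts cancel and the bias in the difference is zero.

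**The case against.** The strongest reply is that the power is discretionary. Section 15 says staff may withdraw a woman; it does not say that a new anticholinergic prescription removes her. A reader might infer automatic removal, and the text does not support that. It does not dispose of the point, because case-by-case judgement by unmasked staff is how selection could enter.

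A reader might also infer that the week-12 OAB-q is definitely not collected. No sentence says so. Section 15 adds that the withdrawal procedure is set out in the consent, which is not in the reviewed text. What stands is that the protocol makes no provision for collecting it. Section 15 also says, citing CONSORT, that everyone assessed for eligibility will be analysed. That sentence sets no follow-up rule and does not fit with the exception in 13.2.

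Further criteria are tempting as examples but carry little weight:
- "Willing to adhere to 12 office visits for PTNS over 3 months if randomized to that arm" looks like a criterion that can be failed in one arm only. Section 12.1.1 largely answers this by keeping women who miss PTNS sessions in the study, and 12.1.2 does the same for TENS.
- "Unable to be contacted for follow up by telephone" mostly describes women already lost to follow-up.
- A current urinary infection can arise later, but nothing in the documents links it to treatment response.
- Withdrawing a woman because her OAB has resolved is a strained reading of criteria that section 4.2 frames as conditions for enrolment.

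Finally, the illustration is one-sided by construction: it assumes removals in one arm only and a deficit of twice the margin. That is fair, and it is why the figures are not an estimate.

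**Conclusion.** The point holds as a defect in a stated rule. Section 15 permits outcome-related removal after randomisation by staff who know the arm. The protocol text neither provides for the primary outcome after such a removal nor defines the woman's place in the intention-to-treat analysis. The anticholinergic criterion alone is enough to show it, and the wish for other treatment in the same sentence is a second route to the same removal.

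The documents do not allow the size or direction of any bias to be computed. The rates of about 8–13% against a nominal 5%, or about 5–8% against 2.5%, rest on four assumptions: 5–10% of TENS women removed, a 20-point deficit, no matching removal in PTNS, and an SD back-solved from 40 per group. The change should be made prospectively, since outcomes not collected at week 12 cannot be recovered later. This concerns data collection and analysis only; no position is taken on clinical management.

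**What to change.** In section 15, limit the eligibility ground to women found not to have met 4.2 at the time of randomisation. State that an entry-type condition arising later, or a wish for other treatment, is recorded as a post-randomisation event, and that any treatment decision is separate from study participation.

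State that the week-6 and week-12 OAB-q and diary are still collected unless the woman refuses further data collection, and that she is analysed in her randomised arm. Under 12.1.1, PTNS questionnaires are completed on a clinic tablet at treatment sessions, so specify remote completion through REDCap for women whose sessions have stopped.

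Align the exception in 13.2 with this rule, and reconcile sections 12.1.1, 12.1.2, 13.2 and 15 so that they give one account of who is followed and who is analysed. Changing only the eligibility ground would leave the other-treatment ground and the 13.2 exception open.

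The cost is a few sentences, matching consent wording and a small amount of remote follow-up. No assessment is added beyond those in Table 1.
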